9.5.2 Analysis of secondary/clinical comes

For comparison of secondary/clinical outcomes we will use the Wilcoxon rank-sum test to compare continuous variables and the likelihood ratio chi-square to compare proportions of categorical variables. Our prior work suggests that there are no significant differences in effects by subgroups categorized by comorbidity or gender. Consequently, we do not plan any subgroup analysis.

Describe the descriptive and inferential statistical methods that will be used to analyze the outcomes and other study data. Specify any confounding variables for which it is anticipated adjustment will be made.

In accordance with NIH policy, unless data from prior studies strongly support no significant differences of clinical or public health importance in the intervention effect between gender and racial/ethnic subgroups, investigators should include a statement noting that a valid analysis of the intervention effect will be performed in these subgroups. If data from prior studies do not strongly support the existence of significant differences in the intervention effect between subgroups, then the analyses need not have high statistical power for detecting clinically meaningful differences.

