1.2 Secondary Objectives

Generate preliminary comparisons between the two study arms, to inform design of a larger multisite trial. Clinical outcomes that will be measured include:

- (1) Quality of life
- (2) Physical function
- (3) Cognitive function
- (4) Pain
- (5) Postoperative complications
- (6) Operative and anesthesia times
- (7) Recovery time (time spent in the post-anesthesia care and stepdown units)

We hypothesize that there will be sufficient data to estimate effect size (based on

means/medians and dispersion) for these key outcomes.

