9.1.3 Justification for pilot design

The chances of completing a successful multisite randomized clinical trial are increased by testing study procedures and processes on a smaller scale prior to conducting a fully powered trial.^{18,19} This will enable us to identify and address problems prior to initiating the fully powered study. Conducting a pilot study also allows us to test study instruments and potentially reduce the time burden at each evaluation visit by determining whether study measures are statistically redundant (the other measures explain a substantial portion of one measure's variance). Reducing the time burden for participants is an important step to enhance the completeness of data collection by minimizing missing data and reducing withdrawals from the study.

As outlined below and in the attached grant proposal, data from the pilot study will also be used for preliminary estimation of effect sizes for the future randomized trial. As the pilot is, by definition, not fully powered to detect all relevant differences between groups, this analysis is entirely exploratory.

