9.1.4 Primary outcomes and hypotheses

- 1) Outcome: Rates of enrollment
 - a. Hypothesis: Based on our preliminary data, at least 75% of eligible patients will agree to be randomized.
- 2) Outcome: Proportion of participants completing all study visits
 - a. Hypothesis: We will be able to follow 100% of patients up to their 2 week postoperative visit (as essentially all patients keep this appointment in our clinical practice), and we will be able to follow at least 90% of patients at the six month time point.
- 3) Outcome: Proportion of missing data
 - a. Hypothesis: Missing data on study instruments will be <5%
- 4) Outcome: Time to complete study evaluations and instruments
 - a. Hypothesis: Total time to complete each study evaluation will be acceptable to patients and <30 minutes.
- 5) Outcome: Participant satisfaction with study procedures and instruments
 - a. Hypothesis: Overall time burden for instrument completion will be acceptable to patients

- 6) Outcome: Whether survey instruments can be eliminated due to redundancy
 - b. Hypothesis: One or more study instruments can be eliminated (thus reducing the time burden) because the other instruments may predict a substantial portion of variance
- (7) Outcome: Estimate sample size for fully powered randomized trial.
 - a. Hypothesis 1: Using data from the pilot study, we will be able to establish stable estimates of the necessary sample size for a randomized trial.
 - b. Hypothesis 2: We will be able to identify the optimal primary outcome for a multisite randomized trial by balancing the necessary sample size needed to adequately power the study versus the clinical significance of each outcome.

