 - a. Measurement: At each visit, after completing all other study forms and procedures, participants will be asked to complete a brief 10-item Likert-type score to measure overall satisfaction with the study visit and a similar item assessing satisfaction with the time burden of the instruments. Additionally, we will conduct a brief interview with open-ended questions at the end of each visit asking patients to provide any feedback on the study procedures or instruments. These will not be recorded but field notes by the research assistant will be taken.
 - b. Timing: Assessments will occur at each study visit and will be reviewed at the last team meeting of each month.
 - 6) Outcome: Whether survey instruments can be eliminated due to redundancy
 - a. Measurement: To determine whether we can reduce the survey burden by eliminating redundant measures, we will employ methods outlined by Harrell for data reduction.²² Each survey instrument will be evaluated as the dependent variable in a separate linear regression with the scores of all other instruments used as predictors, along with demographic information. The adjusted R^2 (explained variance) for each regression will be estimated. Any instrument where the R^2 exceeds 40% will be eliminated based on the idea that little additional information is provided by including that instrument (i.e. the other surveys explain a substantial portion of the information contained within that instrument).
 - b. Timing: We will assess survey redundancy once 25% of planned enrollment is achieved and we will measure again at 75% enrollment. This will provide reasonable data stability for estimation and also provide time for us to test study procedures after eliminating any instruments that are found to be redundant.
 - 7) Outcome: Estimating sample size for fully powered trial
 - a. Measurement: For continuous variables, we will estimate means and standard deviations. For categorical variables, we will estimate proportions and 95% confidence intervals.
 - b. Timing: Final sample size estimate will be performed after data collection for the last patient is complete.

Table 2. Analysis of primary (pilot) outcomes		
Outcome	Measurement	Timing
Rate of enrollment and percent of eligible patients enrolled	
 Running count and graph of planned versus actual enrollment 	Team meeting (every other week)

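### Section 9.5.2 plans only an unadjusted rank test for continuous clinical outcomes, with no between-arm difference and interval, although the pilot exists partly to estimate effect sizes and every outcome instrument has a baseline score

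*Combined protocol and SAP*

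**What the plan says.** Section 9.5.2 gives one method for continuous clinical outcomes: "we will use the Wilcoxon rank-sum test to compare continuous variables". Categorical outcomes get a likelihood ratio chi-square. No covariate appears, and the template instruction left in that section, "Specify any confounding variables for which it is anticipated adjustment will be made", has no answer.

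The stated purposes go further than testing. Section 1.2: "We hypothesize that there will be sufficient data to estimate effect size", to be based on means or medians and dispersion. Section 9.1.3: "data from the pilot study will also be used for preliminary estimation of effect sizes for the future randomized trial", with the qualification that "this analysis is entirely exploratory". Section 9.1.4, item 7, expects to "identify the optimal primary outcome for a multisite randomized trial by balancing the necessary sample size" against clinical significance.

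The only estimation text is section 9.4.1, item 7: "For continuous variables, we will estimate means and standard deviations". It does not say whether these are by arm. Proportions get 95% confidence intervals; continuous outcomes get none.

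The Carolinas Comfort Scale (CCS), Katz, CAM, MoCA, Trail Making and pain scores are all taken at baseline (sections 6.1, 6.2.2 and 9.4.2). Randomisation is blocked within site-by-age strata (sections 3.5 and 9.2.1).

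**The concern.** A rank-test p-value gives neither the size of a difference nor its uncertainty. The plan's own yardsticks are differences: 0.5 SD for most instruments and 3 points for the MoCA (section 9.4.2), and 30 minutes and 5 CCS points (section 9.2.2). Results cannot be read against these unless a difference and its interval are reported.

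The analysis also leaves aside two things already in hand: the baseline scores and the stratification factors. Where baseline predicts follow-up, using it narrows the interval at no cost.

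At stake is the quality of what the pilot hands to the multisite trial, including the choice of its primary outcome. If no estimator is fixed in advance, raw scores, change scores and medians all remain open once the data are seen.

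**Working it through.** **Inputs from the documents.** 40 per arm (9.2.1). Important difference 0.5 SD for most instruments (9.4.2). A 30-minute difference with SD 45 minutes (9.2.2). At least 90% followed at six months (1.1, 9.1.4), so 36 per arm.

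**Assumed.** Two-sided 5% level (sidedness is not stated); baseline-to-follow-up correlation r of 0 to 0.7; blocks of four; the floor shares; the variance explained by strata.

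**The plan's own figure.** n per arm = 2 × (1.960 + 0.842)² × (45/30)² = 35.3, so 36; 36/0.9 = 40 per arm, 80 in total. The stated sample size reproduces with about 10% attrition. With all 40 per arm, power is 84.6% by the normal formula and 81.8% for a simulated Wilcoxon test. The sample size is not in question.

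**Precision.** In SD units, half-width = t × √(2/n) × √(1 − r²). At n = 40, 1.991 × √(2/40) = 0.445, and multiplying by √(1 − r²) gives 0.425, 0.386 and 0.318 at r = 0.3, 0.5 and 0.7. Simulation with blocked randomisation in four strata and a linear model on arm, baseline, site and age stratum agrees:

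| Per arm | Unadjusted | r = 0.3 | r = 0.5 | r = 0.7 |
|---|---|---|---|---|
| 40 | 0.44 | 0.43 | 0.39 | 0.32 |
| 36 (90% retained) | 0.47 | 0.45 | 0.41 | 0.34 |
| 30 (dropped at 75% enrolment) | 0.52 | 0.50 | 0.45 | 0.37 |
| 10 (dropped at 25% enrolment) | 0.93 | 0.94 | 0.85 | 0.70 |

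At r = 0 and 40 per arm the adjusted half-width is 0.45, so adjustment does not help. The last two rows arise because "We will assess survey redundancy once 25% of planned enrollment is achieved and we will measure again at 75% enrollment", and section 9.5.1 drops a redundant instrument for later participants.

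**Power for 0.5 SD, 40 per arm.** Wilcoxon about 57%, t-test about 60%, adjusted model 64%, 72% and 87% at r = 0.3, 0.5 and 0.7. Adjustment itself adds about 4, 12 and 27 points; the other 3 come from changing the test.

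**Scales with a floor.** For a 0-6 score with 70% at the floor, the half-width is 0.44 unadjusted and 0.44, 0.42 and 0.38 adjusted at latent r = 0.3, 0.5 and 0.7 (observed r 0.20, 0.37 and 0.56). With 85% at the floor it is 0.44 against 0.45, 0.43 and 0.39. The adjusted test holds its level (4.9-5.3% null rejection).

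**Times, which have no baseline.** The unadjusted half-width is 0.445 × 45 = 20 minutes. If strata explain 0, 5, 10 or 20% of the variance, the stratum-adjusted half-width is 0.44, 0.43, 0.42 or 0.40 SD. Under the null the planned Wilcoxon test rejects 4.9, 4.6, 3.9 and 3.0% of the time: valid, but conservative as strata matter more.

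**Multisite planning.** For 80% power at 0.5 SD, n per arm from a t-test with effect 0.5/√(1 − r²) is 64 unadjusted and 59, 49 and 34 at r = 0.3, 0.5 and 0.7, if that trial adjusts. The pilot's own r will be imprecise. An observed 0.5 in 80 patients has a Fisher interval tanh(0.549 ± 1.96/√77) = 0.31 to 0.65, which corresponds to 58 down to 38 per arm.

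**The case against.** The strongest reply is that little is missing. Section 1.2 says that effect size will come from means or medians and dispersion, and section 9.4.1 plans means and SDs, from which an unadjusted difference and interval follow. The primary outcomes are feasibility measures, the clinical comparison is declared exploratory and unpowered, and the Wilcoxon test is valid. Important differences are fixed in advance, so sizing the next trial on them needs at most an SD. The gain from adjustment rests on correlations that the documents do not give, and it disappears at low r or in small samples and shrinks on floor-heavy scales. Trail Making scores are already normalised for age and education. The unanswered template line is weak evidence, since such text is left throughout. One interval per instrument and visit makes about 25, with no order of priority.

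Much of this stands, and it limits the point to precision and reporting. Early postoperative pain may gain little, since baseline is typically taken 4-6 weeks before surgery. But a summary from which a reader could derive a difference is not a specified estimate, and 9.4.1 does not say that its means are by arm. Section 9.1.3 commits the pilot to effect sizes, not only SDs. The case for reporting a difference with its interval does not depend on r. Normalising one instrument for age leaves the site factor and the other instruments untouched. The number of intervals is acceptable in an analysis labelled exploratory.

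**Conclusion.** The concern holds. For continuous clinical outcomes the plan specifies a valid but unadjusted test and no between-arm difference with an interval, although estimating effects is a stated purpose and the baseline scores and strata are collected anyway. This should be corrected, but neither the validity of the trial nor its feasibility outcomes depend on it.

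The gain in precision at 40 per arm is negligible at r = 0.3, about 13% at r = 0.5 (0.44 to 0.39 SD by the formula factor √(1 − 0.25) = 0.87) and about 29% at r = 0.7 (factor 0.71). All of this rests on assumed correlations. The reporting gap exists whatever they prove to be.

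**What to change.** - **Section 9.5.2:** for each instrument and visit, report the between-arm difference with 95% interval, adjusted for baseline score, site and age stratum. For operative, anesthesia and recovery times, adjust for strata only. Keep the Wilcoxon test as the robustness check, particularly for Katz and CAM. For complications, keep the likelihood ratio test and add a risk difference with 95% interval.
- **Section 9.5.3:** name the adjusted difference as the quantity pooled after imputation. The section refers to pooling without saying what is pooled.
- **Section 9.4.1, item 7:** beside the raw SD, report the baseline-to-follow-up correlation with its interval, or the residual SD. Use it for planning only if the multisite trial will itself adjust for baseline.
- **Visit list:** the Katz index is scheduled at 48 hours in sections 6.1 and 6.2.3 but not in 9.4.2. Reconcile these so that the set of estimates is defined.

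Separately, and not part of the weight given to this point, the Précis says that there will be no stratification by site and age, while sections 3.5 and 9.2.1 say that there will be. The bands 65-75 and 75+ both contain age 75. Reconcile the sections, make the bands non-overlapping, and document the rule actually used for patients aged exactly 75; a stratum-adjusted analysis needs this settled.

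The cost is wording only. No new data, visits or participants are required.

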9.5.3 Missing data

A complete-case analysis will be performed for the primary analysis of survey and other data. To test sensitivity of the survey results to missing data, we will use multiple imputation with either Poisson or negative binomial regression (depending on overdispersion). For instruments scored by time to completion, we will employ multiple imputation with chained equations. Analysis will then proceed using post-imputation methods that take into account the variance of imputed values across samples (i.e. “pooling rules”).

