9.4.2 Secondary outcomes

Timing of measurements for secondary outcomes is outlined in the schedule of evaluations (section 6.1). Instruments are briefly summarized in [Table 3](#) below.

- 1) Outcome: Quality of life
 - a. Measurement: The Carolinas Comfort Scale (CCS) was developed specifically to measure quality of life in patients having hernia repair.²³ The instrument consists of 8 items on a 6-point Likert-type scale. The Cronbach's alpha was 0.979 in the original development paper and 0.95 on a subsequent international validation study.²¹ The CCS demonstrates superior discrimination when compared to generic quality of life instruments (SF-36), with reasonable test-retest reliability (kappa coefficients for questions range from 0.40-0.60 for all but 1 item. Additionally, the CCS is used as the primary quality of life instrument for the International Hernia Mesh Registry because it can be rapidly administered, is well accepted by patients, is highly reliable, and typically has only 10-15% missing data when used for the international registry.²¹ The CCS can be scored as a summary of all items and as a binary score for the presence or absence of symptoms. We will use a 0.5 standard deviation difference on the continuous scale as the minimal clinically important difference.²⁴
 - b. Timing: The CCS will be measured at baseline, 48 hours after surgery, at 2 weeks after surgery, and at 6 months after surgery.
- 2) Outcome: Physical function
 - a. Measurement: We will measure independence in activities of daily living with the 6-item Katz Index, a long-established measure for physical/functional status for individuals expected to have at least some degree of disability.²⁵ Prior work demonstrates coefficients of scalability ranging from 0.74-0.88, indicating the Katz Index offers a useful cumulative scale.²⁵ We will score the instrument on a 0-6 scale, indicating the number of activities where the participant is partially or fully dependent. A 0.5 standard deviation difference will again represent the minimal clinically important difference.²⁴
 - b. Timing: Measurement will occur at baseline, at 2 weeks after surgery, and at 6 months after surgery.
- 3) Outcome: Cognitive function and delirium
 - a. Measurement

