 - i. Confusion Assessment Method (CAM) short form: The CAM is the most widely used instrument for detection of delirium, with typical sensitivity of 94% and specificity of 89% across multiple studies.²⁶ The instrument is scored on a 7-point scale and we will consider a 0.5 standard deviation difference as the minimal clinically significant difference.²⁴ Items include evaluation of attention, disorganized thinking, and altered levels of consciousness.
 - ii. Montreal Cognitive Assessment (MoCA) 5-minute form: The MoCA is a widely used tool for detection of dementia and other cognitive impairment, and is sensitive when used as a global cognitive screening tool.²⁷ The 5-minute form was developed to (1) reduce the significant time burden of the longer version which typically takes 15 minutes to complete, while (2) maintaining the psychometric advantages of the longer form, and (3) facilitating assessment by

telephone rather than in-person interviews. The instrument evaluates memory/attention, language fluency, orientation, and recall. The 5-minute MoCA has strong correlation with the full version ($r=0.87$), maintains the discrimination of the full version (area under the curve 0.78 versus 0.75 for full version, $p>0.05$), and has strong test-retest validity (intraclass correlation coefficient 0.89).²⁷ Since the 5-minute MoCA was also developed for testing by phone or in person, it meshes with our protocol plans to conduct immediate and long-term follow up by phone. A difference of 3 points is typically considered clinically significant.²⁷

- iii. Trail Making Tests Parts A and B: The Trail Making Test is one of the most popular neuropsychological tests for detecting processing speed, attention, and visual scanning.²⁸ Part A requires participants to draw a line between circles containing numbers, and the circles must be connected in numerical order. Part B is similar, but alternates letters and numbers (1, A, 2, B, et). Both items are scored as time to completion and then normalized to population data based on age and education.²⁸ To address ceiling effects on Part B, we will use the efficiency score for individuals who do not complete the instrument in <300 seconds.²⁹ A 0.5 standard deviation difference in time is considered clinically significant.²⁸
 - b. Timing: All measures will be administered at baseline, prior to discharge, at 48 hours after discharge, at 2 weeks after surgery, and at 6 months after surgery
- 4) Outcome: Pain

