- a. Measurement: We will use a 10-point visual analog scale to measure overall pain levels. A 0.5 standard deviation will be considered a clinically significant difference.
 - b. Timing: Overall pain will be measured at baseline, prior to discharge, at 48 hours after surgery, at 2 weeks from surgery, and at 6 months from surgery.
- 5) Outcome: Postoperative complications
- a. Measurement: All complications will be recorded based on VA Surgical Quality Improvement Program definitions.³⁰ For complications not defined in VASQIP, definitions are also provided below.
 - i. Allergic reaction: if patients develop hives (raised red lesions) or a significant and persistent rash after administration of local or general anesthesia, this will be managed per the usual hospital protocol. Patients will receive a combination of epinephrine, corticosteroids, and antihistamines. Any patient with an allergic reaction will also be admitted for 24 hour observation that includes monitoring of vital signs, and blood pressure support with intravenous fluids. If the allergic reaction occurs during the operation, then the surgery will be canceled along with all assessments and will be rescheduled after it is determined that the operation can be performed safely without the allergic reaction.
 - ii. Hematoma or seroma: a collection of fluid in the tissues over the

incision site or in the scrotum that is detected on physical exam constitutes either a seroma or hematoma. If minimal symptoms present, this will be managed by observation. If persistent and significant symptoms occur, the seroma/hematoma will initially be managed by aspiration under local anesthesia up to two times. If the symptoms persist after aspiration, then the patient can be taken back to the operating room for surgical evacuation.

- iii. Injury to vessel: during dissection and/or mesh placement, there is the possibility of injury to the femoral or inferior epigastric vessels. If bleeding occurs at these vessels that cannot be resolved by applying pressure, this will be categorized as vascular injury. The inferior epigastric vessel is typically ligated without consequence if injured. Injury to femoral vessels will result in consult to vascular surgery for repair.

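### The sensitivity analysis for missing survey scores imputes bounded scales with Poisson or negative binomial models, which have no upper limit and can give impossible values and the wrong spread

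*Combined protocol and SAP*

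**What the plan says.** Section 9.5.3 sets the order of analyses: "A complete-case analysis will be performed for the primary analysis of survey and other data". For the sensitivity check on survey results, "we will use multiple imputation with either Poisson or negative binomial regression (depending on overdispersion"). Timed tests are treated differently: "For instruments scored by time to completion, we will employ multiple imputation with chained equations". The section gives no upper bound, truncation rule, predictor list or number of imputations. It does not say whether items or total scores are imputed.

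Section 9.4.2 defines the scores:

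- Katz: "We will score the instrument on a 0-6 scale", counting dependent activities.
- CAM: "The instrument is scored on a 7-point scale".
- Pain: "We will use a 10-point visual analog scale to measure overall pain levels".
- CCS: "The instrument consists of 8 items on a 6-point Likert-type scale".

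On the amount of missing data, section 9.1.4 has the hypothesis "Missing data on study instruments will be <5" per cent and expects at least 90% follow-up at six months. Section 9.4.2 cites 10-15% missing for the CCS in an international registry.

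**The concern.** Poisson and negative binomial models describe counts without an upper limit. Each of these scores has a maximum, so an imputed value can be one that no patient could record.

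Spread is the second problem. Poisson sets the variance equal to the mean, and negative binomial can only increase it. The stated rule chooses between them by overdispersion, so a score with a high mean and a small SD has no suitable branch.

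Section 9.5.3 names no other check on the complete-case analysis. The pilot is also meant to supply means and SDs for sizing the multisite trial (section 9.4.1, item 7), and section 9.4.2 sets the important difference at 0.5 SD for several instruments. A wrong imputed variance acts directly on those quantities.

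**Working it through.** **Plan figure.** Section 9.5.3 states no number to reproduce. The power statements in section 9.2.2 do not bear on this point, except that the CCS statement implies an SD. A 5-point difference with 80% power, 40 per arm and two-sided 5% (sidedness assumed) gives SD = 5 / [(1.96 + 0.84) × √(2/40)] ≈ 8.0.

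**Assumptions.** Katz 0-6 is stated. CAM 0-7, pain 0-10 and CCS 0-40 (8 items coded 0-5) are assumed codings, and all means are assumed. The range of the 5-minute MoCA is not given, so it is left out. I read survey results as all instruments that are not timed.

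**Step 1: draws above the maximum, P(Y > maximum), with no predictors.**

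| Score | Poisson mean: share impossible |
|---|---|
| Katz, max 6 | 1: 0.01%; 2: 0.5%; 3: 3.4%; 4: 11.1% |
| CAM, max 7 | 2: 0.1%; 4: 5.1% |
| Pain, max 10 | 3: 0.03%; 5: 1.4%; 7: 9.9% |
| CCS, max 40 | 20: 0.003%; 30: 3.2% |

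Negative binomial: CCS with SD 8 and mean 8-20, 0.5-1.5%; pain with SD 2.5 and mean 3-5, 1.3-2.6%; Katz with mean 2 and SD 2, 3.5%. At a Katz mean of 0.5 or less, Poisson gives essentially none.

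**Step 2: simulated imputation.** 40 per arm, 20 imputations, integer scores held within the scale, baseline correlation 0.6, missing more often at high baseline. Patients with missing scores then have higher predicted means, so the impossible share exceeds that in step 1.

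| Assumed score, 15% missing in each arm | Model | Impossible | SD of imputed values (truth) | 95% CI coverage, arm difference |
|---|---|---|---|---|
| 0-40, mean 30, SD 4 | Poisson | 9.4% | 5.8 (3.6) | 98.7% |
| 0-10, mean 7, SD 1.5 | Poisson | 17.5% | 2.8 (1.3) | 98.7% |

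A CCS-like score with mean 10, SD 8 and 15% missing fails in opposite directions. Poisson intervals are too narrow (coverage 91.2%, SE ratio 0.88). Negative binomial over-spreads (9.1% impossible, coverage 98.8%). With SD 8 the variance is 64, above any mean possible on a 0-40 scale, so the overdispersion check should select negative binomial.

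Further simulations with 10-15% missing gave 4.5-12% impossible draws. Coverage ran from 91.7% (CCS-like, Poisson) to above 99% (high-mean score). Under negative binomial a CCS-like SD was 11.1 against a true 8.2. Predictive mean matching (PMM) gave no impossible values and 94-96% coverage.

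**Step 3: values affected.** 5% of 80 is 4 scores and 15% is 12. At 5-12% impossible, that is 4 × 0.05 = 0.2 to 4 × 0.12 = 0.5 per imputed data set, or 12 × 0.05 = 0.6 to 12 × 0.12 = 1.4. The worst case is 12 × 0.175 = 2.1.

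**Step 4: consequence for sizing.** In the 0-40, mean 30 case the extra imputed variance is 5.82² − 3.62² = 33.9 − 13.1 = 20.8. Ignoring the small shift in means, with 15% imputed this adds 0.15 × 20.8 = 3.1 to a true variance of 3.98² = 15.8, about 20%. With 5% imputed it adds 0.05 × 20.8 = 1.0, about 7%. Required sample size rises in proportion, if the imputed data are used for sizing.

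**Step 5: the alternative.** 0-40 score, SD 7.9, true difference −4.92, 15%/5% missing by arm:

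| Method | Bias in difference | Arm-mean coverage (arm with more missing) | Impossible |
|---|---|---|---|
| Complete case | +0.56 | 90.2% | 0% |
| Poisson | −0.34 | 93.4% | 6.2% |
| PMM, 1 / 5 / 10 donors | +0.09 / +0.18 / +0.27 | 91.8 / 92.3 / 92.7% | 0% |
| Normal model | −0.02 | 94.0% | 2.6% |

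The SD of PMM-imputed values was 6.1-6.3 against a true 6.9. At 30%/10% missing, PMM bias was +0.12 to +0.52 and arm-mean coverage 88.7-89.5%. At 5% missing in both arms, bias was at most 0.05 and coverage 94.5-95.2%.

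**The case against.** Several points on the other side stand.

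- Only a sensitivity analysis is affected, and section 9.1.3 calls the between-group analysis exploratory.
- The rank-sum test in section 9.5.2 treats an over-maximum value simply as a top rank.
- Katz is a count of dependent activities, and near its floor a Poisson model is adequate. No document shows any of these scores clustering near its maximum; low pain scores are also little affected.
- An impossible value does little harm by itself. Normal-model imputation also produced some (2.6%) with almost no bias. The variance misfit does more damage.

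Three stronger readings are tempting and are not supported. A reader might infer that the imputation could create or hide a treatment difference. In the simulated 15%/5% case the Poisson bias was smaller than the complete-case bias, and no reversal was shown. A reader might infer that using different methods for surveys and timed tests ignores their correlation. Section 9.5.3 lists no predictors, so it neither includes nor excludes them. A reader might also take PMM to be free of cost. In this sample size it is not: it cannot impute beyond observed scores, and more donors increased the bias.

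The misfit remains. The rule has no branch for underdispersion, and the rank-sum test does not protect means and SDs.

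**Conclusion.** The concern holds as a minor one. The plan names a method that does not suit bounded scores. With 10-15% missing and the assumed distributions, about 5-12% of draws are impossible in most cases, and confidence intervals can be too narrow (coverage about 91%) or too wide (about 99%). Below 5% missing, about four scores per instrument and visit are imputed and the effect is small. It is larger at the 10-15% cited for the CCS. At six months, 90% follow-up would itself leave 0.10 × 80 = 8 scores missing.

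The sizing consequence applies only if imputed data feed the sample-size estimate, which section 9.4.1 does not settle. All sizes rest on assumed codings, means and missingness patterns; only the Katz range and the CCS SD of about 8 come from the plan.

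**What to change.** In section 9.5.3:

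- State the range of each score and whether items or totals are imputed.
- Replace the count models with chained equations for all instruments, using PMM with a stated small donor number, or an ordinal or binomial model (binomial out of 6 suits Katz).
- Name the predictors: arm, baseline and other-visit scores, site and age stratum.
- State the number of imputations, and how rank-sum results are combined, since pooling rules are built for estimates with standard errors.
- Say whether the means and SDs for sizing come from observed or imputed data, and report both.

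The cost is one paragraph of wording and no new data; chained equations are already planned for the timed tests. The plan should acknowledge that with about 40 per arm PMM stays within observed scores, slightly narrows the spread and can leave a small bias if missingness is heavy.
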